- 5 days of CIVIL-2 are superior to 3-day cycles with respect to CD4+ T-cell expansion (32) but cycle duration longer than 5 days or every 4 week versus every 8 week cycles using CIVIL-2 (30) or subcutaneous rIL-2 were associated with increased adverse effects without additional CD4+ T-cell expansion.
- Subcutaneous rIL-2 7.5 million international units (MIU) induces significantly higher CD4+ T-cell increases than 1.5 MIU, although 4.5 MIU doses are biologically active (33-36).
- CD4+ T-cell count increases can be sustained for up to 5 years without adverse effects on steady state HIV-1 plasma RNA levels and often with reduced dosing cycle frequency (31, 37-40).
- In summary, these phase II studies demonstrated that the cyclical administration of subcutaneous rIL-2 (4.5–7.5 MIU per dose) twice daily for 5 consecutive days every 8 weeks with a background of ART resulted in large increases in CD4+ T-cell count, minimal changes in plasma HIV viral load and no significant changes in CD8+ T-cell count (41).

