The purpose of this pilot study is to observe the effects of up to eight 8-weekly cycles of subcutaneous recombinant interleukin-2 (SC rIL-2) on levels of replication-competent HIV in blood CD4 T cells in 20 participants with chronically suppressed HIV infection (viral load <50 copies/mL) who are stable on the same ART regimen for at least one year and have a CD4 T cell count ≥ 350 cells/mm³. We hypothesize that IL-2 administration will result in a reduction of the replication-competent reservoir, as measured by the QVOA assay, compared to the baseline values in this population.

B.1. STUDY ENDPOINTS AND OUTCOME MEASURES

The primary endpoint of the study is the change in the level of replication-competent virus from baseline to the end of rIL-2 treatment, as measured by the Quantitative Viral Outgrowth Assay (QVOA).

B.2. PRIMARY OBJECTIVE

The primary objective will be to compare levels of replication competent HIV in circulating CD4 T cells before and after up to 8 cycles of rIL-2 administration. The frequency of CD4 T cells containing replication-competent virus in leukapheresis samples obtained at baseline and at the end of rIL-2 treatment will be enumerated using several state of the art methods. The primary readout for this objective will be measurement of replication-competent virus by Quantitative Viral Outgrowth Assay (QVOA) performed by [name]'s group at Accelevir.

B.3. SECONDARY OBJECTIVES

- 1) To examine the relationships between levels of replication competent HIV as identified by QVOA and other measures of HIV persistence:
 - a) the intact proviral DNA assay ([name]),
 - b) the Envelope Detection by Induced Transcription-based Sequencing (EDITS, [name]) performed on the same pre-trial and post-trial leukapheresis samples.
- 2) To explore the effects of rIL-2 administration on induction of HIV expression in vivo as measured by the EDITS assay and plasma HIV levels.
- 3) To examine the effects of rIL-2 administration on natural killer cell phenotype and function and on the ability of NK cells to limit HIV propagation in vitro.

C. METHODS

C.1. STUDY DESIGN

This is an open label pilot study of 20 participants with chronically suppressed HIV infection (viral load <50 copies/mL), stable on an ART regimen for at least one year, who have a CD4 T cell count ≥ 350 cells/mm³. All participants will receive rIL-2.

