3. Acute or chronic hepatitis B infection, defined as a positive HBV surface antigen or a positive HBV DNA.
4. History of advanced chronic liver disease, including cirrhosis, advanced liver fibrosis, severe portal hypertension, or manifestations or hepatic failure.
5. History of malignant disease that is not considered to be surgically or medically eradicated or that has required any form of therapy in the past 5 years.
6. Current diagnosis of congestive heart failure of any severity, uncontrolled angina or uncontrolled arrhythmias.
7. History of lung disease that has required pharmacologic treatment, oxygen supplementation, medical monitoring, or hospitalization in the previous year, or that is expected to cause persistent or recurrent pulmonary symptoms or impairment. Examples of the latter include but are not limited to chronic bronchitis, emphysema, and pulmonary fibrosis.
8. History or any features on physical examination indicative of a bleeding diathesis.
9. History or current diagnosis of thromboembolic disease, including deep vein thrombosis and pulmonary embolism, or family history of the same.
10. History of hypersensitivity to radiological contrast media or anticipated need for exposure to radiological contrast media during the study period.
11. Use of chronic corticosteroids, hydroxyurea, or immune-modulating agents (e.g., interleukin-2, interferon-alpha or gamma, granulocyte colony stimulating factors, etc.) within 30 days prior to enrollment.

NOTE: Use of inhaled or topical steroids is not exclusionary.

12. Breast-feeding.

13. Use of aspirin, warfarin or any other antithrombotic or antiplatelet agent during the 2-week period prior to leukapheresis.
14. History of autoimmune disorders, including but not limited to Crohn's disease, scleroderma, thyroiditis, inflammatory arthritis, myasthenia gravis, glomerulonephritis, systemic lupus erythematosus, and vasculitis.
15. Type 1 diabetes mellitus.
16. History of thyroid disease requiring that has required antithyroid or thyroid hormone replacement therapy at any time in the past.
17. Current continued use, or anticipated continued medical indication for nephrotoxic agents, including but not limited to aminoglycosides and other potentially nephrotoxic antimicrobials, indomethacin, high scheduled doses of other NSAIDs, and lithium salts.
NOTE: Low doses or limited duration of these agents (i.e., ≤ 14 days) is not exclusionary.

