18. Current continued use, or anticipated continued medical indication for hepatotoxic agents, including but not limited to amiodarone, methotrexate, and anticonvulsants and antimicrobials with elevated hepatotoxic potential.
NOTE: Low doses or limited duration of these agents (i.e., ≤ 14 days) is not exclusionary.
19. Active drug or alcohol use or dependence that, in the opinion of the investigator, would interfere with adherence to study requirements.
20. Serious illness requiring systemic treatment and/or hospitalization within 30 days prior to study entry that in the judgement of the investigator may compromise study participation or pose additional risks to the participant.
21. Any other condition that, in the opinion of the clinical investigator or sponsor, might compromise any aspect of this trial.

C.5. STUDY TREATMENT PLAN

C.5.1. Study Medication (rIL-2)

Proleukin® (Prometheus Laboratories) is provided as a sterile, white to off-white, lyophilized cake in glass vials, each containing 22 MIU.

C.5.1.1. Dosage and Cycle Guidelines

Participants will receive rIL-2 at an initial dose of approximately 5 MIU twice daily for 4 consecutive days every 8 weeks (8 cycles total). Each vial will be reconstituted according to the package insert instructions using 1.2 mL of diluent, and 4 doses will be obtained from each vial. Occasionally, the reconstituted volume that can be drawn from the vial may result in doses that are slightly smaller than 5 MIU each. These small deviations from the total intended dose are biologically inconsequential and do not constitute protocol deviations.

C.5.1.2. Preparation of rIL-2 for Subcutaneous Administration

The Investigational Pharmacy will reconstitute rIL-2 at the beginning of each cycle for each participant, and draw each individual dose into tuberculin syringes under sterile conditions. As was done in two previous large trials of rIL-2 in HIV-infected participants(19), all eight doses will be prepared, labeled, and delivered to the participant on day 0 of each cycle. This procedure may be modified in the course of

the study if deemed necessary by the Investigational Pharmacy, the investigators, or a regulatory authority, including the option to prepare a smaller number of doses in advance. In that case, pre-filled syringes may be shipped by fast courier to the participant's residence.

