Medication Category	Timeframe
Antiretroviral medications	Complete history
Immune-based therapies	Within 90 days prior to study entry
Vaccines	Within 30 days prior to study entry
All other prescription and non-prescription medications	Within 90 days prior to entry

D.3.4. Clinical Assessments

D.3.4.1. Complete Physical Exam

A complete physical exam is to include at a minimum an examination of the skin, head, mouth, and neck; auscultation of the heart and lungs; abdominal exam; and examination of the lower extremities for edema. The complete physical exam will also include vital signs (temperature, heart rate, respiration rate, and blood pressure).

D.3.4.2. Targeted Physical Exam

A targeted physical exam is directed to the site or organ system involved in any previously identified or new signs or symptoms that the participant has experienced since the last visit. This exam also includes vital signs (temperature, heart rate, respiration rate, and blood pressure).

D.3.4.3. Height

Height without shoes in centimeters will be obtained at screening and recorded on the CRF at entry.

D.3.4.4. Weight

Weight without shoes in kilograms will be obtained at screening, leukapheresis visit, at

entry and at day 0 of each cycle. The weight obtained at entry and at day 0 of each cycle will be recorded on the CRF.

D.3.4.5. Interval History

At entry, all signs and symptoms, regardless of grade, that occurred within 45 days before entry will be recorded in the source documents. Post-entry, only grade ≥ 2 signs and symptoms, or those that led to a change in treatment, regardless of grade, will be recorded on the corresponding CRFs.

D.3.4.6. Diagnoses

After study entry, all new diagnoses established while on study will be recorded on the source document. Any gradable diagnoses that meet AE criteria will be recorded on the CRF, and relationship to study agent will be assessed.

D.3.4.7. Concomitant Medications

Concomitant prescription or over-the counter medications initiated or discontinued since the last visit will be recorded on the source documents.

D.3.4.8. Study Treatment Modifications

All study drug modifications, including actually administered doses preceding each of the scheduled in-person or phone assessments will be recorded. Any permanent discontinuation of treatment will be recorded on the CRF.

D.3.4.9. Antiretroviral Medications

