The SMC will review accrual, toxicity summaries, off-treatment and off-study rates, and reasons broken down by study arms. Meetings of the SMC are described above. The SMC will be asked to consider the following regarding safety events: the grade of the event, the time to resolution (if any), and the site clinician's judgment of the relationship to treatment. The first interim safety review by the SMC is planned 3 months after the first subject enrolls and approximately every 3 months thereafter, but expedited reviews will occur whenever the threshold for temporary enrollment discontinuation is reached. Criteria for temporary enrollment discontinuation and expedited SMC review are:

- Three or more participants have experienced a grade 3 AE that is deemed possibly, probably, or definitely related to study treatment
- Two or more participants have experienced a grade 4 AE that is deemed possibly, probably, or definitely related to study treatment
- Any death occurs on study that is deemed possibly, probably, or definitely related to study treatment

The SMC will review the events whenever any of the criteria above is met, and recommend, based on the results of the review, whether the study can proceed as planned, proceed with modifications, or be discontinued.

I.4. Human Subjects Involvement, Characteristics, and Design

Up to 20 participants will be enrolled in the clinical trial. Potential participants will be recruited primarily from the Special Immunology Unit, the HIV clinic of University Hospitals Cleveland Medical Center, although recruitment from other area hospitals through direct outreach and targeted advertisement is also possible. Characteristics of the study population, inclusion/exclusion criteria, and planned study procedures are described in the clinical protocol. No vulnerable populations will be included in these studies.

I.5. Sources of Materials

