In ESPRIT, there was an excess of grade 4 clinical events in the rIL-2 recipients; the same excess was not seen in SILCAAT. Abrams and colleagues (42) have suggested this is via an impact on procoagulant pathways. In ESPRIT, patients with the highest CD4+ T-cell counts in the rIL-2 arm had the greatest relative risk of clinical events, including death. Perhaps, therefore, receipt of rIL-2 primes the patient for a proinflammatory state subsequently associated with more clinical events, and this is amplified in patients with the greatest CD4+ T-cell response to rIL-2, i.e. the ESPRIT cohort, which had higher baseline CD4+ T-cell counts than in SILCAAT. However, it is still important to remember that while rIL-2 receipt in ESPRIT was associated with more embolic

events, overall there was no excess of opportunistic diseases, death or cardiovascular disease and non-AIDS cancers compared with the ART-only arm.

I.6.1.1. Risk Mitigation Strategy for Serious Infections

Although there was no increased risk of infections in the two large phase III clinical trials of IL-2 administration (SILCAAT and ESPRIT), to mitigate the risk of serious infections, individuals with any of the following conditions will be excluded from enrolling in this study:

- A screening CD4 T-cell count <350 cells/mm³
- An absolute neutrophil count <1500 cells/mm³
- An active local or systemic infection
- Use of immunosuppressive or immune modulating therapy
- Use of any investigational agent
- Actively co-infected with HBV or HCV

If a serious infection develops, study drug will be held until the infection is adequately controlled. Study drug administration will be interrupted if the ANC is <1,000 cells/mm³.

I.6.1.2. Risk Mitigation Strategy for Hypersensitivity Reactions

To mitigate the risk of hypersensitivity reactions including anaphylaxis:

- Patients with a known allergy/sensitivity or any hypersensitivity to components of the study drug or its formulation will be excluded.
- The first dose of study agent will be administered in the Special Immunology Unit that has treated more than 50 patients with IL-2 on SILCAAT and ACTG 328 trials. Subjects will be monitored for a minimum of 30 minutes following the first dose of study drug by personnel with life support training and access to adequate life support equipment and resuscitation medication.
- A severe allergic reaction related to study treatment will be grounds for study treatment discontinuation.

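### A 30-day bar on earlier IL-2 and a 90-day medication look-back let former IL-2 recipients enrol unrecorded, so some baselines may already be lowered and the before-after change biased toward no effect

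*Combined protocol and SAP*

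**What the plan says.** Item 11 of the exclusion criteria, in C.4 and in the synopsis, groups IL-2 with corticosteroids, hydroxyurea and other immune modulators. The bar covers "interleukin-2, interferon-alpha or gamma, granulocyte colony stimulating factors, etc.) within 30 days prior to enrollment". No criterion names IL-2 received before that window.

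Table 1 in D.3.3 asks for a full antiretroviral history, but for immune-based therapies the timeframe is "Within 90 days prior to study entry". The covariates named in C.2.1 do not include earlier IL-2.

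Section B states the hypothesis: "We hypothesize that IL-2 administration will result in a reduction of the replication-competent reservoir", judged against baseline. Under C.1 every participant receives rIL-2. I.4 says that participants will be "recruited primarily from the Special Immunology Unit, the HIV clinic of University Hospitals Cleveland Medical Center", with other area hospitals also possible. I.6.1.2 places the first dose in the "Special Immunology Unit that has treated more than 50 patients with IL-2 on SILCAAT and ACTG 328 trials".

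Two other lines bear on the point. I.6.1.1 lists "Use of immunosuppressive or immune modulating therapy" among its exclusions, with no time window. Item 21 of C.4 excludes "Any other condition that, in the opinion of the clinical investigator or sponsor, might compromise any aspect of this trial".

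**The concern.** A 30-day window may suit clearance of the drug. It does not suit the effect that the trial is looking for. If IL-2 shrinks a pool of cells that A.1 calls long-lived, a person treated years ago may enter with a reservoir that is already reduced and has little room to fall.

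In a single-arm trial the baseline sample is the only comparator, so such a person pulls the estimated change toward zero. The same person also blurs C.2.1(b), which models the number of IL-2 cycles received and looks for a threshold: that section does not mention IL-2 given before the trial, so on-study cycles would understate lifetime exposure. Because the history taken need not go back beyond 90 days, the analyst might be unable to identify or adjust for these participants.

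**Working it through.** **1. The plan's own figure.** C.2.2 gives 80% power at N=20 for a fall of 0.64 IUPM with variance 0.41; the synopsis gives the same power at N=16. No alpha is stated, so two-sided 0.05 is assumed. Taking two independent readings per person, the variance of the change is 2 × 0.41 = 0.82. Power by normal approximation is Φ(0.64/√(0.82/N) − 1.96).

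- N=16: 0.64/0.226 = 2.83, power 80.7%.
- N=20: 0.64/0.202 = 3.16, power 88.5%.

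The synopsis version reproduces; the C.2.2 version does not. That mismatch is a separate matter. N=20 is used below because it is the planned enrolment.

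**2. How many former recipients might be at the assay floor.** A.2 reports 8 of 14 IL-2-treated people at or below the detection limit, against 1 of 12 on ART alone. The excess is 8/14 − 1/12 = 0.571 − 0.083 = 0.488.

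**3. Dilution of the mean change.** Let k of 20 be former recipients (k is assumed; the documents do not give it). Suppose that the excess share at the floor cannot fall further and everyone else shows the full fall. Dilution is then 0.488 × k/20:

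- k=2: 0.488 × 0.10 = 4.9%.
- k=4: 0.488 × 0.20 = 9.8%.

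If no former recipient falls further, dilution is k/20: 10% and 20%.

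**4. Effect on power at N=20.** Let f = k/20 and let r be the fraction of the 0.64 fall that former recipients still show. The mean change is 0.64(1 − f + fr). Its variance is 0.82 + f(1 − f)[0.64(1 − r)]².

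| k | r | Mean change (IUPM) | Power (normal) |
|---|---|---|---|
| 0 | – | 0.640 | 88.5% |
| 2 | 0.5 | 0.608 | 84.8% |
| 4 | 0.5 | 0.576 | 80.4% |
| 2 | 0 | 0.576 | 79.5% |
| 4 | 0 | 0.512 | 68.2% |

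The r=0.5 rows have 5% and 10% dilution, so they stand close to the floor-rate case in step 3. Powers from the noncentral t distribution are 3.5 to 4.6 points lower throughout. If only 16 were analysed, the r=0 figures would be 67% (k=2) and 53% (k=4), from 81% with none.

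**5. Does another line close the gap?** The I.6.1.1 line has no window and can be read as current use only. Item 21 is discretionary and does not mention IL-2. Neither says that past IL-2 excludes, and I.6.1.1 does not match the 30 days in item 11.

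**The case against.** The strongest reply is that the exposed group may be empty. The figure of more than 50 is offered in E.1.2 and I.6.1.2 as evidence of experience in giving IL-2, not as a count of current clinic patients. SILCAAT enrolled at CD4 counts of 50 to 299 and was reported in 2009 after years of follow-up, while this protocol cites a 2019 paper, so that exposure is probably a decade old or more. Former recipients must now be 65 or younger, have a CD4 count of at least 350, and pass the thyroid, autoimmune and thromboembolic criteria. This stands: k could be zero.

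Several stronger readings are tempting, but the documents do not support them.

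- *That the hypothesis is a lasting reduction.* Section B says only that the reservoir will be reduced from baseline. Durability is inferred from A.1's description of the pool. The study in A.2 is cross-sectional, and no time since the last IL-2 dose is given.
- *That A.4 shows persistence.* Its statement that "CD4+ T-cell count increases can be sustained for up to 5 years" concerns CD4 counts, not the reservoir, and goes on to mention less frequent cycles, so it does not describe what happens after IL-2 stops.
- *That the data could not reveal the problem.* QVOA on the baseline leukapheresis would show floor-level values. The IL-2 antibody test at cycle 1 day 0 could flag some earlier exposure, since A.5 reports non-neutralizing antibodies in 66% to 74% of treated patients. Neither replaces a history: a low QVOA value does not give its cause, and how long antibodies last is not stated.
- *That investigators have no way to exclude former recipients.* Item 21 lets them, and I.6.1.1 arguably does, but neither requires it.
- *That dilution follows from the raw 8/14.* That would give 5.7% and 11.4%, but it ignores the 1 in 12 at the floor without IL-2.

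**Conclusion.** The gap in the eligibility and history rules is real; its consequence is conditional. The plan can admit people with earlier IL-2, need not record it, and has no control arm to absorb the effect. Any resulting bias runs toward no effect.

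For two to four former recipients among 20, dilution of the mean change is about 5% to 10%, or 10% to 20% if they show no further fall. In the milder case the calculated power stays at or above 80% by normal approximation; with four complete non-responders it drops to about 68%.

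These figures rest on an assumed k, on an earlier reduction having persisted, and on the floor rate of the older assay (limit 0.03 IUPM) carrying over to the optimized QVOA, whose floor is not stated. A reader should not conclude that any baseline is in fact already treated. The point is that the plan leaves this possible, and that closing the gap is cheap.

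**What to change.** 1. In C.4 item 11 and the matching synopsis item, separate IL-2 from the other agents and exclude any previous receipt of it.
2. Reconcile the undated immune-modulator line in I.6.1.1 with item 11, so that both state the same rule.
3. In Table 1, extend the IL-2 history to lifetime: number of cycles and date of the last one.
4. If any former recipient is enrolled, keep that person in the primary analysis, because C.2.1 defines the intent-to-treat population as everyone with at least one dose. Pre-specify a sensitivity analysis without such participants, for both the primary change and the cycles-received model.

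The cost is a line in each eligibility list, an edit to I.6.1.1, a row in Table 1, one extra analysis, and the loss of a few otherwise eligible candidates. If enrolment has finished, steps 3 and 4 can still be done, with the sensitivity analysis specified before the QVOA results are analysed.
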